12.2 Statistical Methods

12.2.1. Specific Aim #1. *To determine whether randomization to a weight reduction program results in greater reductions in frequency of incontinence episodes at 6 months compared to the control condition.*

Analysis. Our hypothesis is that randomization to the weight reduction group will result in greater reductions in frequency of incontinence compared to the control group. The predictor variable is assignment to the weight loss or control group and the outcome is change from baseline to the end of the weight loss intervention at 6 months in number of incontinent episodes per week, as recorded on the 7-day voiding diary. As described above, we will use mixed linear regression models to compare average changes in the intervention and control groups, controlling for clinical center and taking account of clustering within weight loss groups.

Sample size estimation. In our pilot study of weight loss for treatment of incontinence, the between-group difference in reduction in incontinence frequency was 12 episodes per week (average reductions of 14 vs 2 episodes in the weight loss vs. control groups), with standard deviation (SD) of 14 episodes per week, for a very large standardized effect size of nearly 0.9 SDs. In the proposed study, expected weight loss will be smaller and the control group will receive a self-help booklet that will likely result in some improvement in

incontinence; furthermore the pilot study was small, providing imprecise estimates. Thus, we conservatively assume a smaller net reduction in incontinence frequency of 6 episodes per week in the weight reduction compared to the control group, half the effect seen in the pilot study but large enough to be clinically meaningful. This corresponds to a standardized effect size of .43 SDs, assuming an SD of 14 episodes per week for the changes in frequency. We also assume that 10% of the sample will drop out before the 6-month visit; with imputation of baseline values for missing post-randomization incontinence frequencies, this attenuates the effect size in proportion to the dropout rate. Finally, we assume that clustering within the small intervention groups will induce a moderate design effect of 1.3. We adapted standard methods for two-sample comparisons of a continuous outcome to account for the design effect as well as the attenuation of the treatment effect size by imputation of baseline values. Under these assumptions, a sample of 330 women will provide at least 80% power in two sided tests with alpha of 5% to detect between-group differences of 6 incontinence episodes per week. Small to moderate gains in power may be obtained by the use of repeated measures, depending on the level of within-subject correlation.

12.2.2. Specific Aim #2. *To determine if randomization to a motivation-based maintenance program results in less weight regain from 6 to 18 months compared to a skill-based maintenance program.*

Analysis. Our hypothesis is that motivation-based weight maintenance will result in less weight regain than skill-based weight maintenance over the 12 months of the intervention. The predictor variable is random assignment to the motivation-based weight maintenance program compared to skill-based weight maintenance or control group, and the outcome is change in weight from the end of the weight reduction program at 6 months to the end of the maintenance period at 18 months. As in Specific Aim #1, we will use mixed linear regression models for change in weight over the maintenance period, controlling for group, degree of weight loss during the weight loss period, and taking account of clustering by weight loss group.

Power estimates. Conservatively assuming a loss to follow-up of 15% between 6 and 18 months, the sample of 220 women randomized to motivation-based or skill-based maintenance strategies will provide 80% power to detect between-group differences in weight loss of 0.56 standard deviations. In prior TRIM

weight loss studies,⁷³ the standard deviation of weight loss at 18 months in the skill-based behavioral treatment condition was 6.8 kg, so that the minimum detectable between-group difference in average weight loss at the end of the study will be less than 3.8 kg.

12.2.3. Specific Aim #3. *To identify women who are most likely to experience improved continence after weight reduction, based on factors such as initial body mass index, body fat distribution and type of incontinence (stress, urge or mixed).*

Analysis. Our hypothesis is that some subgroups of women (defined by baseline body weight, body mass index, waist circumference, or type of incontinence), will be more likely to have improvement in incontinence with weight loss compared to others. Analyses in subgroups defined by these baseline variables will be similar to those described for Specific Aim #1. These subgroup analyses constitute comparisons between randomized groups, and are only mildly affected by the multiple comparisons problem. We will test for subgroup by treatment interactions.

Power estimates. Under the same assumptions used for Specific Aim 1, subgroups comprising 50, 40, or 30% of the sample will provide 80% power to detect standardized effects of approximately 0.58, 0.63, and 0.75 SDs, respectively, corresponding to changes of 8.5 to 10.5 episodes of incontinence per week.

12.2.4. Specific Aim #4 *To determine if randomization to a weight reduction program results in greater improvement in continence from baseline to 18 months compared to control and whether the motivation-based maintenance program results in greater improvements in continence than the skill-based maintenance program or control from baseline to 18 months.*

Analysis. Our hypotheses are that the weight reduction program will result in lower frequency of incontinence overall than in the control condition, and that motivation-based weight maintenance will result in lower frequency of incontinence than skill-based weight maintenance during the 18 months of follow-up. The predictor variables are random assignment to the weight

reduction program or to the motivation-based weight maintenance program compared to skill-based weight maintenance, or to the control group, and the outcome is change from baseline to the end of the weight loss intervention at 18 months in frequency of incontinence episodes. Analyses will be similar to those described above for specific aim 1.

12.2.5. Specific Aim #5. *To determine if randomization to a weight reduction program results in greater improvement in quality of life from baseline to 6 and 18 months compared to the control condition.*

Analysis. Our hypothesis is that randomization to a weight reduction program will result in greater improvements in quality of life measures than to a control condition at both 6 and 18 months of follow-up. The predictor variable is assignment to the weight reduction or control groups and the outcome is change in quality of life outcomes including Incontinence Impact Question (IIQ), Urogenital Distress Inventory (UDI) and Short Form-36 (SF36), from baseline to 6 and 18 months. Analyses will be similar to those described above for specific aim 1. In addition to the primary analysis comparing weight reduction to a control condition, we will also make pairwise comparisons between motivation-based maintenance, skill-based maintenance, and the control condition at 18 months.

Power estimates. Under the assumptions used for Specific Aims 1 and 2, the sample of 330 women will provide 80% power to detect actual treatment differences of 0.43 SDs in the primary comparison between weight loss and control at 6 months, and 0.49 SDs at 18 months. In pairwise comparisons between the three groups at 18 months, we will be able to detect differences of 0.56 SDs. These are small to moderate differences, as shown below.

Instrument	SD of single measures	Minimum detectable difference in changes**
UDI	50 ⁵⁹	22-28
IIQ	60 ⁵⁹	26-34
SF36 PCS*	25-30 ⁶³	16-18
BDI	4.5 ⁷⁴	19-25

* Physical component scale

** Assuming within-subject correlation of repeated measures of 0.5

In all cases, smaller between group differences in change would be detectable if within-subject correlation exceeds 0.5.

12.3 Exploratory analysis of potential mechanisms for improvement in incontinence with weight loss. A series of closely related mixed linear models will be used to assess mechanisms by which the weight reduction intervention potentially affects measured incontinence frequency as well as related quality of life measures. We will first assess modification of the effects of treatment by baseline urodynamic measurements of leak point and intravesical pressures, to determine if the effectiveness of the weight reduction intervention varies by these parameters. To maximize efficiency, effect modification will be assessed as a continuous interaction between treatment assignment and the urodynamic measures. We will then examine the overall effects of assignment to the weight reduction group on the urodynamic measures as well as weight loss, to show the effect of the intervention on the proposed mediators. Next, we will use repeated measures models to determine the association between change since baseline in the proposed mediators and current incontinence frequency, to show that changes in the mediator are associated with changes in the primary outcome, and to determine which of the proposed mediators independently predict change in incontinence frequency. Finally, we will examine the attenuation of the estimated effect of treatment on incontinence frequency after controlling for changes in the proposed mediators, as an estimate of the proportion of the treatment effect explained. Confidence intervals for proportion of the treatment effect explained will be computed.⁷⁵

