weight loss studies is to impute baseline outcomes for observations missing due to dropout, substantially reducing bias due to "non-ignorable" missingness.^{71, 72} A slight drawback of this procedure is that such singly imputed values are treated as known, so that standard errors on average are too small. To address this potential source of inferential error, we will use multiple imputation of the baseline outcomes with an additive error term derived from the repeated measures model estimate of within-subject residual error. The analysis will then be carried out in the multiple datasets, and the results combined using standard methods to produce summary effect and standard error estimates that properly incorporate the imputation error.^{71, 72} As a sensitivity check, we will also carry out a secondary analysis without imputation, but adjusted for baseline covariates, under the assumption that the data are missing at random ⁷¹ given treatment assignment, the observed outcome values, and baseline predictors of outcome.

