The primary aim of PRIDE is to determine if modest weight loss results in improvement in urinary incontinence among obese and overweight women with incontinence. The weight loss intervention includes standard approaches to diet and behavioral change that have been used successfully in many prior studies. An important secondary aim is to determine if a motivation-based weight maintenance program results in improved weight maintenance compared to a skills-based weight maintenance program. This intervention is innovative for weight maintenance, but the elements of this motivation-based program have been used in other successful behavioral interventions. PRIDE investigators believe that both the weight loss and weight maintenance interventions are safe. Investigators will carefully track potential serious adverse events that will be reviewed at each DSMB in-person meeting or conference call. If evidence of serious harm emerges, the PRIDE DSMB may decide to alter or stop the study at any time for safety concerns.

2. Stopping or Altering PRIDE for Efficacy

PRIDE investigators expect that, compared to usual care, the weight loss intervention will result in an average of 6% weight loss (about 6 kg) over 6 months and that this change in weight will result in a reduction of about 6 episodes of incontinence per week. There is no scientific or ethical reason to stop or alter the study if this intervention proves to be more effective than expected.

The expected efficacy of the innovative weight maintenance program is less clear, but PRIDE investigators believe that participants randomized to the skills-based program will regain about 1/3 of the weight lost, while those in the motivation-based program will regain no weight. There is no scientific or ethical reason to stop or alter the study if this intervention proves to be more effective than expected.

Thus, as long as no safety issues arise, PRIDE will not be stopped or altered if the interventions are unexpectedly effective.

3. Stopping or Altering PRIDE for Futility

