Answering the main PRIDE research question requires that the weight loss intervention result in greater weight loss in the intervention compared to the usual care group. Based on effects in prior trials, participants in the weight loss group are expected to lose 6% of their body weight (6 kg), compared to no loss in the usual care group. However, the effect of this degree of weight loss on frequency of incontinence is not clear, and is the main question in PRIDE.

If the 6-month weight loss intervention does not result in substantial weight loss, we cannot address the main PRIDE research questions. If no weight loss occurs, we cannot determine if weight loss leads to an improvement in urinary incontinence; similarly, if no weight loss occurs, we cannot determine if a motivation-based weight loss maintenance program is more effective than a skills-based program. Thus, if weight loss is less than expected in the weight loss group, the DSMB will give consideration to altering the intervention and to stopping the trial.

Stopping or altering PRIDE for futility will be based on estimates of the efficacy of the weight loss intervention at the point when approximately 75% of the participants have completed the program. Efficacy for weight loss will be assessed as the difference between the weight loss and usual care groups in change in weight from baseline to the end of the 6-month intervention period. Efficacy for improvement in incontinence will be assessed as the difference between the weight loss and usual care groups in change in number of incontinence episodes per week from baseline to the end of the 6-month intervention period. The analyses of these outcomes, as specified in the protocol, will use a random effects model for piece-wise linear mean trajectories for average weight and frequency of incontinence in the treatment and control groups. These analyses will not require alpha-spending.

At this interim analysis, consideration will be given to stopping the study for futility if the point estimate of the difference between the weight loss and standard care groups is not 4 kg or greater. The DSMB might consider continuing the study even if efficacy for weight loss is low *if* the intervention has resulted in an improvement in incontinence of at least 20% or greater. In this case, changes in dietary composition or exercise habits might be responsible for an improvement in incontinence.

C. OTHER CONSIDERATIONS

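### The 80% power stated for primary Aim 2 overlooks the small number of randomised counselling groups and sits at nearly twice the difference the trial expects; the Aim 2 model sentence also needs correcting

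*Protocol*

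**What the plan says.** Section 3.1 lists Aim 2 as a primary aim. Section 12.2.2 defines its outcome as weight change from month 6 to month 18. It states that 220 women, with 15% loss to follow-up between those visits, give 80% power at 0.56 SD. The conversion to kilograms rests on earlier studies in which "the standard deviation of weight loss at 18 months in the skill-based behavioral treatment condition was 6.8 kg", and leads to the statement that "the minimum detectable between-group difference in average weight loss at the end of the study will be less than 3.8 kg".

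The analysis paragraph of the same section reads: "The predictor variable is random assignment to the motivation-based weight maintenance program compared to skill-based weight maintenance or control group". The model is described as "controlling for group, degree of weight loss during the weight loss period, and taking account of clustering by weight loss group".

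The DSMB guidelines (Operations Manual, Appendix 3B, Appendix II) expect about 6 kg lost at six months. They then say, after conceding that the efficacy of the maintenance program is uncertain, that "participants randomized to the skills-based program will regain about 1/3 of the weight lost, while those in the motivation-based program will regain no weight". Section B.1 of that appendix describes the maintenance comparison as a secondary aim.

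**The concern.** The power statement raises three difficulties.

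- The second randomisation allocates whole counselling groups (section 8.2.2). A design effect of 1.3 inflates the variance but does not allow for the few groups from which the between-group variation must be estimated.
- No expected difference is set against the 3.8 kg. The only figure the documents supply, one third of 6 kg against none, is about 2 kg, and 3.8/2 = 1.9.
- The SD quoted is the unadjusted SD of loss at 18 months, whereas the planned analysis is of 6-to-18-month change adjusted for 6-month loss.

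The model sentence has two faults. It brings in the control arm, which takes no part in the second randomisation, while conditioning on 6-month weight loss; for any contrast with control, that covariate is measured after randomisation. It also controls for group, where section 12.1.1 and the parallel sentence for Aim 1 specify clinical center.

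At stake is how a null result would be read. Against an 80% claim it would look like evidence of no useful difference, when the test may have had much less power for the effect the investigators had in mind.

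**Working it through.** **Inputs.** From 12.2.2: 220 women (110 per program), 15% loss from month 6 to 18, SD 6.8 kg. From 12.2.1, assumed to carry over: two-sided 5%, 10% loss before month 6, design effect 1.3, effect attenuated in proportion to dropout.

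**Reproducing 0.56 SD.** Retention factor 0.90 × 0.85 = 0.765. Standard error in SD units = √(1.3 × 2/110)/0.765 = 0.1537/0.765 = 0.201. Detectable difference = (1.960 + 0.842) × 0.201 = 0.563 SD, against 0.56 stated. The same factors give 0.488 SD for weight loss against control at 18 months, matching the 0.49 in 12.2.5. So the figure reproduces, and it uses normal quantiles.

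**Number of groups.** Appendix III of the DSMB guidelines plans 336 women in sets of 84, with 14 women in each of 3 groups at 2 sites. That is 336/84 = 4 waves × 2 sites × 2 weight-loss groups = 16 groups, or 16 − 2 = 14 df. Noncentrality at 0.56 SD is 0.56/0.201 = 2.79; with a t reference on 14 df, power is 74%. For 80% the noncentrality must be 3.013, so the detectable difference is 3.013 × 0.201 = 0.606 SD, or 4.12 kg at SD 6.8. Section 8.2.2 allows 10 to 20 women per group, that is 220/20 = 11 to 220/10 = 22 groups (9 to 20 df); power at 0.56 SD is then 70% to 76%.

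**Expected difference.** Appendix II: 6 kg × 1/3 = 2 kg. Section 9.3 expects 7-9% loss; at 100 kg (assumption, implied by the appendix equating 6% with 6 kg) one third of 7-9 kg is 2.3-3.0 kg.

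**Relevant SD.** Regain equals 6-month loss minus 18-month loss. With 6-month loss as a covariate, regressing regain or 18-month loss on program gives the same program effect (sign reversed) and the same standard error. The SD that matters is therefore the residual SD, 6.8 × √(1 − r²), where r is the within-arm correlation of 6- and 18-month loss. The documents do not give r; the values below 6.8 kg are assumptions.

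**Power**, with noncentrality = difference/(residual SD × 0.201), design effect and retention held fixed:

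| r | Residual SD (kg) | 2 kg, normal | 2 kg, t 14 df | 3 kg, normal | 3 kg, t 14 df |
|---|---|---|---|---|---|
| 0 | 6.8 | 31% | 28% | 59% | 53% |
| 0.5 | 5.9 | 39% | 35% | 72% | 65% |
| 0.7 | 4.9 | 54% | 48% | 87% | 82% |
| 0.8 | 4.1 | 68% | 62% | 96% | 92% |

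On normal quantiles, 80% power at 2 kg needs a residual SD of 2/0.563 = 3.55 kg; with 14 df it needs 2/0.606 = 3.30 kg. Both are about half the only SD cited.

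**The case against.** The strongest defence is that 12.2.2 reports a detectable difference and nowhere claims 80% power at 2 kg. The 2 kg comes from DSMB guidance, is introduced there as uncertain, and is not a design assumption. The covariate also makes 6.8 kg conservative. On normal quantiles the 3.8 kg bound holds once r exceeds about 0.07 (0.12 using 0.563); even with 14 df it holds once r exceeds about 0.39, since 3.8/4.12 = 0.923 and √(1 − 0.923²) = 0.385. The choice of reference distribution can be left to an SAP, and 16 groups is a planning figure. All of this stands as far as it goes. It does not rescue 80% at 0.56 SD for a comparison of so few groups, and it leaves power at the expected effect unstated.

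A reader might infer more, which the documents do not support:

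- *That power is simply about 30%.* That is the worst case, at the unadjusted SD.
- *That 6.8 kg belongs to the wrong outcome and invalidates the figure.* With the 6-month covariate the two outcomes give the same test, so it is an upper bound.
- *That 0.56 × 6.8 = 3.81 contradicts the stated bound.* This is rounding.
- *That the dropout rule in 12.1.2 ("we will use multiple imputation of the baseline outcomes with an additive error term") scores women lost before month 6 as having no regain and so distorts the comparison.* Sections 1.0 and 4.0 place the second randomisation after completion of the weight-loss program, so their inclusion is unsettled. If included, they left before assignment and only dilute the contrast. The 0.90 factor already allows for that; without them the figure is 2.802 × √(1.3 × 2/99)/0.85 = 0.534 SD.
- *That controlling for group removes the program effect.* That needs counselling group as a fixed effect, which the text does not say. The same sentence names clustering by weight loss group separately, so a slip for clinical center is likelier.

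**Conclusion.** The point holds in moderate form and should be fixed; it is not a fatal flaw. The 0.56 SD is correctly computed on its own terms, but 80% becomes about 74% once the reference distribution reflects roughly 16 groups, and 80% then needs about 0.61 SD. The stated 3.8 kg is nearly twice the 2 kg in the DSMB appendix and above the 2.3-3.0 kg implied by section 9.3. At 2 kg, power runs from 31% (28% on 14 df) at SD 6.8 to 68% (62%) at r = 0.8. At 3 kg it passes 80% only if r is high, about 0.7 or more on 14 df. These ranges rest on the protocol's design effect and retention, Aim 1's alpha carrying over, 16 groups, a 100 kg mean weight for the upper differences, and assumed values of r.

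The model sentence is wrong as written. The aim, hypothesis and 220-woman basis all concern two programs, so control does not belong in the comparison. The primary and secondary labels for this aim also conflict.

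**What to change.** In the power paragraph of 12.2.2, state power at the expected 2 to 3 kg difference over a range of residual SDs for the adjusted 6-to-18-month change, with degrees of freedom taken from the number of counselling groups. Say that 6.8 kg is an unadjusted upper bound.

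In the analysis paragraph, delete the reference to the control group so that only the two re-randomised programs are compared, replace group by clinical center as the adjustment variable, and keep 6-month weight loss as covariate and clustering by weight loss group.

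Reconcile section 3.1 with section B.1 of Appendix II on whether this aim is primary or secondary.

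The cost is wording only, with no added participants or visits. The downside is a less favourable stated power.

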3.0 Clinical Trial Objectives

3.1 Primary aims of PRIDE are to:

1. determine whether randomization to a weight reduction program results in greater reductions in frequency of incontinence episodes at 6 months compared to a control condition;
2. determine if randomization to a motivation-based weight maintenance program results in less weight regain compared to a skill-based maintenance program from the end of the weight reduction program (6 months) to the end of the weight maintenance program (18 months);

3.2 Secondary aims are to:

3. identify women who are most likely to experience improved continence after weight reduction, based on factors such as initial body mass index, body fat distribution and type of incontinence (stress, urge or mixed).
4. determine if randomization to a weight reduction program results in greater improvement in continence from baseline to 18 months compared to a control condition and whether the motivation-based weight maintenance program results in greater improvement in continence from baseline to 18 months than the skill-based weight maintenance program or control condition.
5. randomization to a weight reduction program results in greater improvement in quality of life from baseline to 6 and to 18 months compared to a control condition.

3.3 Tertiary aims in a volunteer subset of 100 participants are to:

6. evaluate whether urodynamic measurements can identify women who are most likely to experience improved continence after weight reduction
7. investigate the mechanism by which weight loss improves continence

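### Aim 3 tests effect modification by baseline weight, BMI and waist through subgroups; a continuous interaction would have more power for a roughly linear gradient, by an amount that depends on the grouping and the gradient

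*Protocol*

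**What the plan says.** Aim 3 stands in section 3 of the protocol under "3.2 Secondary aims are to". Section 12.2.3 states its hypothesis in terms of subgroups: "some subgroups of women (defined by baseline body weight, body mass index, waist circumference, or type of incontinence), will be more likely" to improve than others. On method it says "Analyses in subgroups defined by these baseline variables will be similar to those described for Specific Aim #1" and "We will test for subgroup by treatment interactions". Its power paragraph carries over the Aim 1 assumptions and states that "subgroups comprising 50, 40, or 30% of the sample will provide 80% power" to detect "standardized effects of approximately 0.58, 0.63, and 0.75 SDs". No continuous interaction is written for this aim.

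Section 12.3 covers the exploratory work on urodynamic measures, taken in 100 volunteers. There the plan is: "To maximize efficiency, effect modification will be assessed as a continuous interaction between treatment assignment and the urodynamic measures".

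The wording of 12.2.3 and 12.3 is the same in the initial protocol and in the version carrying Amendment 5.

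**The concern.** Three of the four Aim 3 moderators are measurements on a continuous scale, and entry BMI now runs from 25 to 50 kg/m². Grouping them discards the variation within each group. Effect modification is the whole question of this aim, and interaction tests are weak at this sample size. The protocol gives the efficient form to an exploratory analysis in 100 women and the grouped form to a secondary aim in all 330, without a stated reason. What is at stake is a lower chance of detecting a real gradient of benefit across weight, BMI or waist. The categorised form is fixed in the protocol's own text, so this is a stated choice of method and not a detail left open.

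**Working it through.** **Inputs.** 330 women randomised 2:1 (220 and 110), SD of change 14, difference 6 episodes per week, 10% dropout with baseline imputation (effect × 0.9), design effect 1.3, two-sided 5%. All come from sections 8.2.1 and 12.2.1. Carrying the design effect of 1.3 to the interaction is an assumption, following the statement in 12.2.3 that the Aim 1 assumptions apply.

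**1. The plan's own figures.** The standard error in SD units is √(1.3 × (1/110 + 1/220)) = 0.1331.
- Aim 1: 0.9 × 6/14 = 0.386, and 0.386/0.1331 = 2.90. Power = Φ(2.90 − 1.96) = 82.6%, in line with "a sample of 330 women will provide at least 80% power".
- Effect detectable within a subgroup that is a fraction f of the sample: (1.960 + 0.842) × 0.1331/0.9/√f = 0.4145/√f. This gives 0.586, 0.655 and 0.757 SD for f = 0.5, 0.4 and 0.3, against the stated 0.58, 0.63 and 0.75. The 50% and 30% figures agree; the 40% figure is slightly optimistic.

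**2. What those figures measure.** They are treatment effects within one subgroup. The interaction compares two subgroups. With two halves its standard error is twice that of the overall effect, so the difference detectable at 80% power is 2 × 0.4145 = 0.83 SD, or 11.6 episodes per week. The planned overall effect is 6.

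**3. Two-way split against a continuous term.** For a linear gradient over a normal moderator, splitting off a fraction p keeps a relative efficiency E = φ(z_p)²/(p(1−p)). If the continuous test has 80% power, the split has Φ(2.802 × √E − 1.960).

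| Split | E | Power | Loss |
|---|---|---|---|
| 50/50 | 0.637 | 61% | 19 points |
| 40/60 | 0.622 | 60% | 20 points |
| 30/70 | 0.576 | 57% | 23 points |

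A simulation of the median split (4,000 runs, effective n = 254, 2:1) gave 78.8% against 59.8%.

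**4. More groups.** With equal-sized ordered groups and a trend test, E is about 0.79, 0.86 and 0.90 for three, four and five groups. Power is about 70%, 74% and 76% against 80%, a loss of about 4 to 10 points. An unordered test over the same groups would do worse, because it spends extra degrees of freedom on the same signal.

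**5. Shallower gradients.** The standard error of the slope per SD of moderator is 14 × 0.1331 = 1.864 episodes per week. Without dropout attenuation:

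| Gradient per SD | Continuous | Median split |
|---|---|---|
| 2 | 19% | 14% |
| 3 | 36% | 25% |
| 5.2 | 80% | 61% |

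With the 0.9 attenuation, a gradient of 5.2 gives 71% against 52%.

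**6. Distribution and shape.** For a uniform moderator at a median split E = 0.75, so 80% becomes 68%, a loss of 12 points. For a right-skewed moderator the simulation gave 77.6% against 55.9%, a loss of 22 points. If benefit is a step exactly at the median cut, the ranking reverses: where the split has 80%, the linear interaction has about 61%.

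**The case against.** **Stronger readings that the documents do not support.**
- A reader might take the 50, 40 and 30% as the cuts to be applied to weight, BMI and waist. They appear only in the power paragraph, as sizes for detecting an effect within a subgroup, and they have to serve incontinence type as well. Neither the number of groups nor the cut-points are stated for Aim 3, and that detail may properly sit in the statistical analysis plan.
- A reader might see a contradiction between 12.2.3 and 12.3. There is none. One section concerns subgroups in a secondary aim and the other exploratory mechanism work in a substudy, and different questions may use different forms.
- A reader might state a loss of about 20 points as a fact about this trial. That figure needs a two-way split, a linear gradient, a roughly normal moderator and a steep slope. At 5.2 episodes per week per SD around a mean benefit of 6, women 1 SD below the mean would gain 0.8 and women 1 SD above would gain 11.2, and about 12% would do worse on treatment.

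**What else stands on the other side.** At shallow gradients neither test has adequate power. The protocol asserts no linear gradient. If curvature entered the test as a joint two-degree-of-freedom test, power at slope 5.2 would fall from 80% to about 70% and return much of the gain. BMI categories do appear elsewhere: overweight and obese in the background, and 35 kg/m² as an enrolment target in the urodynamic substudy. Neither is tied to Aim 3.

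**What does not stand.** None of this removes the direction of the result: for a roughly linear gradient, the continuous term has more power than the grouped form in every case examined.

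**Conclusion.** The point holds as an inexpensive improvement to a secondary aim. It is not an error or an inconsistency in the protocol. Section 12.2.3 fixes a grouped interaction test for three continuous moderators, and a continuous test has more power if the gradient is roughly linear. The size is conditional on the number of groups, the moderator's distribution, the steepness of the gradient and its shape: from about 4 points (five ordered groups with a trend test) to about 23 points (a 30/70 split), both measured where the continuous test would have 80% power. None of these losses is stated in the protocol; they follow from its Aim 1 inputs and the assumptions named with each figure. The criticism does not extend to incontinence type, which is categorical.

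**What to change.** In section 12.2.3, make the interaction test for baseline weight, BMI and waist a continuous treatment-by-covariate term with one degree of freedom, added to the Aim 1 mixed model. Add a separate curvature check (a quadratic or spline term) as supportive analysis only, so that it does not dilute the test. Keep incontinence type categorical, and keep subgroup estimates to describe the effect at readable levels of weight, BMI and waist.

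The cost is analysis wording: the baseline values are already collected, and no visit, measurement or sample-size change is needed. The downside is reliance on a roughly linear pattern. If benefit truly changes in a step at the chosen cut-point, the linear test is less powerful than the split, and the curvature check and descriptive subgroup estimates are there to show such a departure.
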